7.5.3 Laboratory parameters

All laboratory parameters will be summarized using descriptive statistics. Then, shift tables and absolute changes for each laboratory parameter will be displayed summarizing individual patient changes from baseline to each post-baseline time point. In case of missing value at W0 (baseline) for a variable, imputation will be performed using the value obtained at screening. This imputation method will only be applied for generation of shift tables. Unreportable values will be replaced by 0.

Haematology results will be assessed at screening, W0 (baseline), W4, W8, W16, W24, W32, W40, W48):

- Red blood cell count (10⁹/L)
- Haemoglobin (g/L)
- Haematocrit (%)
- White blood cell count (10⁹/L)
- Platelet count (10⁹/L)

CER-001-CLIN-009 CER-001

- Neutrophils (10⁹/L)
- Lymphocytes (10⁹/L)
- Monocytes (10⁹/L)
- Eosinophils (10⁹/L)
- Basophils (10⁹/L)

Biochemistry results will be assessed at screening, W0 (baseline), W4, W8, W16, W24, W32, W40, W48:

- Glucose (mmol/L)
- Blood urea nitrogen (mmol/L)
- Creatinine (µmol/L)
- Creatinine clearance (mL/min)
- Uric acid (μmol/L)
- Albumin (g/L)
- Total protein (g/L)
- Total bilirubin (µmol/L)
- Indirect bilirubin (μmol/L)
- Creatine Kinase (IU/L)
- Alkaline phosphatase (IU/L)
- AST (SGOT) (IU/L)
- ALT (SGPT) (IU/L)
- Lactate dehydrogenase (IU/L)
- Calcium (mmol/L)
- Potassium (mmol/L)
- Sodium (mmol/L)
- Phosphorous (mmol/L)
- Chloride (mmol/L)
- Total CO2 (mmol/L)

Urinalysis will be assessed at screening, W0 (baseline), W4, W8, W16, W24, W32, W40, W48:

- White Blood Cell (WBC) (per HPF)
- Red Blood Cell (RBC) (per HPF)
- Total protein (positive/negative)
- Glucose (positive/negative)
- Total bilirubin (positive/negative)
- Ketones (positive/negative)
- pH
- Microalbuminuria (mg/L)
- Casts (per LPF)
- Specific gravity

Fasting blood glucose will be summarized at screening, W0, W4, W8, W16, W24, W32, W40 and W48.

In case of abnormal and clinically significant result for a parameter, a by-patient listing of all laboratory values for the parameter during the study will be produced.

Shift tables will be:

- No change (from positive to positive / from negative to negative)
- Improvement (from negative to positive)

CER-001-CLIN-009 CER-001

- Deterioration (from positive to negative)

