#### **SECONDARY SAFETY PARAMETERS:**

- Incidence and severity of AEs from routine monitoring.
- Incidence of abnormalities and changes from baseline in clinical laboratory parameters from testing of blood and urine, including anti-ApoA-1 antibody.

Incidence of cardiovascular events.

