#### **11.7 Liver and kidney expected adverse reactions which may lead to drug withdrawal**

To date, there have been no significant laboratory abnormalities associated with the use of CER-001 in humans, however toxicology studies in mice and monkeys indicate that liver and kidney are possible target organs for toxicity.

Specific requirements for hepatic and renal abnormalities are detailed below.

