### **12.3.2 Analysis of Safety and Tolerance Variables**

Descriptive statistics will be provided for all safety parameters.

Adverse events will be coded by body system and preferred term based on the Med-DRA dictionary of standardized terminology. All AEs reported during the study will be listed, documenting course, severity, relationship to study drug and outcome. Adverse events will be tabulated by study treatment.

Summary tables will give the number and proportion of patients who experienced an AE, broken down by body system, preferred term and maximum severity. Related adverse events, defined as those adverse events that are possibly, probably or definitely related to study drug, will be summarized similarly.

Laboratory parameters, vital signs, physical exam results, and ECG findings will be summarized by treatment group and time point using descriptive statistics (n, mean, standard deviation, median and range), or frequencies and percentages, as appropriate. Results will be classified as normal or abnormal at screening and at on-treatment and follow-up visits. Shift tables of these values will be provided to summarize the change between screening and on-treatment / follow-up for each treatment group.

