7.5.2 Vital signs, physical examination, ECG

Clinical examination and vital signs will be summarized at each time point (screening, W0 (baseline), W4, W8, W16, W24, W32, W40, W48, 4 weeks after last dose). In addition, absolute changes from W0 (baseline) will be calculated at each post-baseline time point. Absolute change at Wi is defined as follows: Value at Wi - Value at W0.

- Respiratory rate (breaths/min)
- Systolic blood pressure (mmHg)
- Diastolic blood pressure (mmHg)
- Heart rate (beats/min)
- Body temperature (°C)
- Body weight (kg)
- Body mass index (kg/m²)

ECG diagnosis (Normal / Abnormal, not clinically significant (NCS) / Abnormal and clinically significant (CS)) will be summarized at screening and presented through shift tables from W0 (baseline) for the following time points: W4, W8, W16, W24, W32, W40, W48, 4 weeks after last dose).

In case of abnormal result regarding ECG (clinically significant or not) for a given patient, a listing will be produced including patient's identification, visit, date of assessment, ECG diagnosis, specification for the result and remarks, whatever the visit.

Assessment of physical examination (Normal / Abnormal non-clinically significant / Abnormal clinically significant) will be described at screening and presented through shift tables from W0 (baseline) for the following time points: W4, W8, W16, W24, W32, W40, W48, 4 weeks after last dose).

In case of missing value at W0 for a variable, imputation will be performed using the value obtained at screening. This imputation will be performed for shift tables only and absolute changes.

Shift tables will be:

- No change (from normal to normal / from abnormal NCS to abnormal NCS / from abnormal CS to abnormal CS)
- Improvement (from abnormal NCS to normal / from abnormal CS to abnormal NCS / from abnormal CS to normal)
- Deterioration (from normal to abnormal CS / from normal to abnormal NCS / from abnormal NCS to abnormal CS)

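### SAP 7.5.3 gives shift categories that fit only 4 of its 40 laboratory tests, so the incidence of laboratory abnormalities is not reliably counted by arm

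*SAP*

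**What the plan says.** SAP 7.5.3 promises that "shift tables and absolute changes for each laboratory parameter will be displayed", from baseline to each later visit. It then gives three categories for these tables: "No change (from positive to positive / from negative to negative"), "Improvement (from negative to positive") and "Deterioration (from positive to negative"). A parameter with an abnormal and clinically significant result goes to a by-patient listing.

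The protocol asks for more:

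- The synopsis lists among the secondary safety parameters "Incidence of abnormalities and changes from baseline in clinical laboratory parameters from testing of blood and urine", and section 8.14.2 repeats this.
- Section 12.3.2 says "Results will be classified as normal or abnormal at screening and at on-treatment and follow-up visits" and adds shift tables for each treatment group. Laboratory parameters are among the data covered.
- Section 11.7 reports no significant laboratory abnormality in humans so far, but says animal toxicology indicates that "liver and kidney are possible target organs for toxicity". It then sets liver and kidney limits.

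The SAP introduction says that the SAP supersedes the protocol and that changes are reported in its section 10. Section 10 records only the change of efficacy model.

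**The concern.** A programmer working from 7.5.3 cannot build most of the tables it promises, and would have to choose a classification that the plan does not state. Because the SAP takes precedence, the workable scheme in protocol 12.3.2 has in effect been replaced by one that does not fit quantitative results, and nothing shows whether this was intended.

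At stake is a descriptive comparison, since no formal tests are planned for safety data. It is nevertheless the comparison meant to deliver a named secondary safety parameter, for organs the protocol singles out. With about 20 patients on CER-001 and 10 on placebo (30 randomized 2:1), one or two patients with a large rise are the likely form of any signal. A count by arm shows such patients more plainly than a mean does.

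**Working it through.** The plan gives no figure on this point to reproduce. The check is a count, followed by a comparison of the texts.

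**1. Tests covered by the stated categories.** SAP 7.5.3 lists 10 haematology, 20 biochemistry and 10 urinalysis parameters: 10 + 20 + 10 = 40. Results are coded positive/negative for urine total protein, glucose, total bilirubin and ketones: 4. Without a usable category: 40 − 4 = 36, and 36/40 = 90%. Fasting blood glucose is listed separately; including it gives 37 of 41. The 36 include ALT, AST, total bilirubin, creatinine and creatinine clearance.

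**2. Direction for the other 4.** For protein, glucose, bilirubin or ketones in urine, positive is ordinarily the abnormal finding. Under the stated labels, new proteinuria would be tabulated as improvement and its disappearance as deterioration. The labels would make sense only if positive meant favourable, which the SAP does not say.

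**3. SAP against protocol 12.3.2.**

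| | Protocol 12.3.2 | SAP 7.5.3 |
|---|---|---|
| Categories | normal / abnormal | positive / negative |
| Starting point | screening | W0, screening if W0 is missing |
| Last time point | follow-up visit | W48 |

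None of these differences appears in SAP section 10.

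**4. Limits in protocol 11.7.** There are eight:

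- Liver function test above 3 × ULN (work-up may be required).
- ALT or AST above 5 × ULN (dose withheld).
- Three discontinuation criteria: ALT or AST above 8 × ULN at first observation, above 5 × ULN for more than 2 weeks, and Hy's Law.
- Three renal criteria: unexplained creatinine above 2 × ULN at two consecutive tests, unexplained creatinine above 1.5 × ULN at three consecutive tests, and creatinine clearance of 30 mL/min or less.

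SAP tables that count patients meeting any of them: 0.

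**5. What adverse event reporting catches.** Protocol 11.1 makes a laboratory result an adverse event if it comes with symptoms, needs further testing or intervention, or changes study or concomitant treatment.

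- Above 5 × ULN, dosing is withheld, so the result should be an adverse event.
- Hy's Law cases and the renal cases are reportable as adverse events under 11.7.
- Between 3 and 5 × ULN, work-up and dose reduction are both optional. If neither happens and there are no symptoms, no adverse event need be recorded.

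For out-of-range results that do not meet its conditions, 11.1 says they are analysed as laboratory abnormalities. The residue is thus sent to the very analysis for which 7.5.3 has no category.

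**6. What the summaries show.** As an illustration with assumed values, take 19 CER-001 patients with ALT at 0.7 × ULN and one at 3 to 5 × ULN:

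- Mean: (19 × 0.7 + 3)/20 = 16.3/20 = 0.815, up to (19 × 0.7 + 5)/20 = 18.3/20 = 0.915 × ULN.
- Median: 0.7 × ULN.
- Maximum: 3 to 5 × ULN.

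The maximum shows that at least one patient was high at that visit. It does not show how many, or how many across the study.

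**The case against.** A reader might infer that laboratory abnormalities are not compared by arm at all, or that patients above 5 × ULN would drop out of sight. The documents do not support either reading:

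- Rises above 5 × ULN, Hy's Law cases and the renal cases should all become adverse events. SAP 7.5.1 tabulates treatment-emergent events by SOC and PT, counts those leading to dose reduction or to temporary or permanent discontinuation, and lists them individually. The Table 5 shell has a column for each arm.
- SAP 7.1.2 includes the minimum and maximum in every quantitative summary, and all data are listed. With 30 patients the listings can be read.
- Section 10 does not withdraw the by-arm shift tables of protocol 12.3.2.
- The Table 10 shell shows normal, abnormal not clinically significant and abnormal clinically significant by arm. Protocol 8.8.4 has investigators rate out-of-range laboratory values for clinical significance. The gap could then be a missing cross-reference.

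The first two points stand and limit the concern to the less severe rises and to counting. The last two do not remove it. No text links Table 10 to laboratory data. Its categories are those of SAP 7.5.2 for ECG and physical examination ("No change (from normal to normal / from abnormal NCS to abnormal NCS / from abnormal CS to abnormal CS")), and 7.5.3 states a different set. If Table 10 were borrowed, it would rest on the investigator's rating and would not separate low from high values. Silence in section 10 does not tell the programmer which of two conflicting schemes to use.

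Reference-range categories with a worst-value table go beyond what protocol 12.3.2 requires. Normal/abnormal would satisfy the protocol; low/normal/high is the more informative form of the same idea.

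**Conclusion.** The point holds in limited form. The shift rule in SAP 7.5.3 fails for 36 of 40 tests, looks reversed for the other 4, and conflicts with protocol 12.3.2 without record. The SAP therefore does not reliably count laboratory abnormalities by arm. The exposed part is results that need not become adverse events, chiefly isolated transaminase rises of about 3 to 5 × ULN; the more severe liver and renal cases should be captured elsewhere.

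This rests on three assumptions: that 7.5.3 means positive and negative as test results, that sites apply the recording conditions of protocol 11.1 as written, and that the separate DSMB analysis plan, which is not among these documents, does not govern the final report. The efficacy analyses are unaffected. The change should be made before database lock, but it does not put the trial's main conclusion in doubt.

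**What to change.** In SAP 7.5.3:

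1. For quantitative tests, define shifts against the laboratory reference range as low / normal / high, by arm, from baseline to each visit and to the worst post-baseline value. Take the lowest and highest values separately and include unscheduled repeats.
2. Correct the direction of the improvement and deterioration labels for the four positive/negative urine tests.
3. Add one descriptive table giving n (%) of patients by arm who meet each limit exactly as written in protocol 11.7. Keep the condition that a creatinine rise be unexplained, and the consecutive-test requirements. Settle which rises count as unexplained at the blinded data review.

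In SAP section 10:

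4. Record any departure from protocol 12.3.2 that is kept, including the starting point and the omitted follow-up visit, or align the SAP with the protocol.

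The cost is SAP wording and two table shells. The central laboratory already measures these parameters, and no new data or clinical threshold is needed.

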## 8.5 Safety Follow-up

### For patients treated until week 48:

Patients will be instructed to fast prior to the visit. A safety follow-up for all patients will be conducted 4 weeks (+/- 7 days) after the final dose of study medication and will include,

- Physical exam (See Section 8.8.1)
- Blood Pressure and Heart Rate
- Vital signs (See Section 8.8.2)
- ECG (See Section 8.8.3)
- Previous and concomitant treatments
- Adverse Events
- Urinalysis (See Section 8.8.4)
- Blood samples for
  - Serum biochemistry (See Section 8.8.4)
  - Hematology and coagulation (See Section 8.8.4)

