#### **8.7 Assessments and Procedures for Patients who Prematurely Discontinue Study Medication during double-blind treatment period**

Patients who withdraw from study medication should come to the site for a safety follow-up, 4 weeks after the last dose: the same safety assessments as the ones planned for study completer's week 52 visit (V31) should be performed.

Additionally:

- In case the study medication is stopped prematurely prior to week 24 (V18), a 3T-MRI should be performed as soon as possible after study drug discontinuation. If the patient agrees to stay in the study, he/she will be asked to come back at the site for full assessments as per protocol every 8 weeks until visit V30 and a last 3T-MRI will be performed at visit V30.
- In case the study drug is stopped during the extension treatment period (i.e. after week 24 (visit V18), patient should come back to the site for full assessments as per protocol every 8 weeks until week 48, a last 3T-MRI will be done at week 48.

All AEs (related or not related) must be reported until the final study evaluation at visit V30 and thereafter only the SAEs likely to be related to the study drug or study procedures must be notified.

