### **8.8.4 Clinical Laboratory Tests**

Laboratory tests should be measured at the screening visit, randomization, at week 4, week 8 and every 8 weeks thereafter until the end of treatment. Additionally, laboratory tests will be done at the follow-up visit. Any blood sample collected according to the Schedule of Assessments (Appendix A) may be analyzed for any of the tests outlined in the protocol. This may also include, but is not limited to, investigation of unexpected results and incurred sample reanalysis.

Clinical laboratory safety testing during the screening and treatment periods will be performed by a central laboratory. Collection kits, shipment instructions, and a detailed clinical laboratory manual will be provided to the study sites. Investigators are required to review the labs upon receipt and make a determination of clinical significance for labs outside of the normal range. All laboratory reports must be reviewed, signed and dated by a medically trained investigator. Clinical laboratory safety testing will consist of the following panels of laboratory tests. The details of which tests are performed at each visit can be found in Appendix A.

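### SAP 7.5.3 ends the laboratory tables at week 48 and, without declaring it, leaves out the visit four weeks after the last dose that the protocol collects and says it will tabulate by treatment group

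*SAP*

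**What the plan says.** **Collection.** Protocol 8.8.4, after giving the laboratory schedule up to the end of treatment, adds: "Additionally, laboratory tests will be done at the follow-up visit". Protocol 8.5, for patients treated until week 48, says: "A safety follow-up for all patients will be conducted 4 weeks (+/- 7 days) after the final dose of study medication". It then lists serum biochemistry, haematology with coagulation, and urinalysis. Appendix A marks these tests and fasting glucose at V31 (W52). For early stoppers, protocol 8.7 says: "Patients who withdraw from study medication should come to the site for a safety follow-up, 4 weeks after the last dose". The assessments are those of the W52 visit.

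**Promised analysis.** Protocol 12.3.2 classifies results as normal or abnormal at screening, on treatment and at follow-up, and continues: "Shift tables of these values will be provided to summarize the change between screening and on-treatment / follow-up for each treatment group".

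**SAP 7.5.3.** The laboratory lists read "Haematology results will be assessed at screening, W0 (baseline), W4, W8, W16, W24, W32, W40, W48", "Biochemistry results will be assessed at screening, W0 (baseline), W4, W8, W16, W24, W32, W40, W48" and "Urinalysis will be assessed at screening, W0 (baseline), W4, W8, W16, W24, W32, W40, W48". Fasting glucose has the same last visit.

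**SAP 7.5.2.** For vital signs, ECG and physical examination the post-baseline points are "W4, W8, W16, W24, W32, W40, W48, 4 weeks after last dose".

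**Precedence.** The SAP introduction states that the SAP overrides the protocol and that changes will be reported in section 10. Section 10 reports only the change of efficacy model.

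**The concern.** The laboratory section of the SAP is narrower than the protocol's collection schedule, the protocol's analysis section and the SAP's own neighbouring section. Because the SAP takes precedence, a programmer working from 7.5.3 would build tables that stop at W48.

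What is at stake is a safety description. Protocol 3.3.1 names liver, spleen and bone marrow as target organs in animals and describes the changes there as reversible. Protocol 11.7 treats liver and kidney as possible target organs. A summary by arm of laboratory values off drug bears directly on that. There is also an internal mismatch. SAP 7.5.1 counts adverse events as treatment-emergent up to 28 days after the last infusion, which is nominally the date of this visit. An adverse event at the visit would be tabulated, but the laboratory values taken there would not.

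**Working it through.** No power or sample-size figure enters this point. The check sets the schedules side by side and then counts.

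**1. Time points for chemistry, haematology, urinalysis and fasting glucose**

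| Source | Screening, W0 | W4, W8, W16, W24, W32, W40, W48 | 4 weeks after last dose | Total |
|---|---|---|---|---|
| Protocol Appendix A | 2 | 7 | 1 | 10 |
| SAP 7.5.3 (laboratory) | 2 | 7 | 0 | 9 |
| SAP 7.5.2 (vital signs and other examinations) | 2 | 7 | 1 | 10 |

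The protocol has 7 + 1 = 8 post-baseline points and SAP 7.5.3 has 7. One of 8 is missing.

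**2. Parameters affected.** SAP 7.5.3 lists 10 haematology + 20 biochemistry + 10 urinalysis = 40 parameters, plus fasting glucose.

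**3. Early stoppers: does the 4-week visit fall on a listed laboratory week?**
- Infusions are weekly from W0 to W8 (9 visits) and then every two weeks. A last dose before W48 can therefore also fall at W10 to W46 (19 visits). In all, 9 + 19 = 28 nominal early last-dose weeks.
- Adding 4 weeks reaches a listed week for last doses at W0, W4, W12, W20, W28, W36 and W44, giving W4, W8, W16, W24, W32, W40 and W48. That is 7 of 28.
- The other 28 − 7 = 21 miss.
- Protocol 8.5 allows ±7 days. Counting every visit that could land on a listed week within that window adds last doses at W1, W3 and W5 (W5, W7 and W9, each one week from W4 or W8). At most 10 of 28 could then match, leaving 18 that cannot.

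The visit therefore usually, but not always, falls outside the listed weeks.

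**4. Who can contribute off-drug values**
- Protocol 6.6 offers open-label CER-001 after W48 to every completer, whatever the arm. Appendix B schedules no laboratory tests in that phase, and protocol 8.5 makes its follow-up a phone call. These patients should have no routine off-drug laboratory values.
- The documents do not say how many will enter the extension, so only a range can be given. As an assumption, take the 20% sample-size buffer as the discontinuation rate: 0.20 × 30 = 6 stoppers and 24 completers, or at 2:1, 4 and 2 stoppers and 16 and 8 completers.
- If all 24 completers enter the extension, at most 6 patients contribute (4 on CER-001, 2 on placebo). If none enters, at most 30 contribute (20 and 10). Missed visits lower both ends.

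**The case against.** **The SAP's general wording may already cover the visit.** The opening of 7.5.3 promises changes and shifts at every time point after baseline. Read alone, that could include follow-up. But the explicit lists that come after it end at W48, and 7.5.2 uses similar general wording while naming the follow-up visit. At best the text is ambiguous.

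**No data are lost.** This is right. SAP 7.7 plans listings of all collected data, and 7.5.3 adds a listing for parameters with a clinically significant abnormal result. A listing does not replace the table by treatment group that the protocol promised.

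**This is not the only evidence on recovery.** A reader might infer that the visit is the sole planned human test of reversibility. The documents do not support that. Under protocol 8.7, early stoppers who stay in the study return every 8 weeks to W48 for full assessments, so their off-drug values do reach the SAP tables. Protocol 8.8.4 has clinically important abnormal results repeated until they settle or are explained. Protocol 8.3 takes samples before dosing unless otherwise specified, so from W16 they are nominally 14 days after the previous infusion, whereas protocol 3.3.1 describes the animal liver-enzyme rises as generally reversing within 24 to 48 hours. Protocol 11.7 adds that no significant laboratory abnormality has been associated with CER-001 in humans so far. All of this lowers the stakes.

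**The table would describe a selected group.** This stands in full: only early stoppers and completers who decline the extension can contribute.

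**Conclusion.** The omission is real, undeclared and out of line with both the protocol and SAP 7.5.2. Its size is one of 8 post-baseline laboratory points, for 40 parameters plus fasting glucose, absent from the descriptive tables by arm. For completers who do not enter the extension it is the only routine off-drug laboratory visit. The primary endpoint is not affected.

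Three stronger readings go too far. Recovery off drug is not left wholly unexamined, for the reasons given above. An early stopper's visit does not always fall off schedule: 21 of 28 nominal last-dose weeks do. And no formal comparison between arms has been removed, because both documents plan only descriptive laboratory summaries.

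The conclusion assumes that the SAP's explicit lists govern the programming and that extension patients have no laboratory tests beyond those in Appendix B. It is worth correcting because the protocol promised the table and the correction is cheap, but the gain is limited by how few and how selected the contributing patients may be.

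**What to change.** - In SAP 7.5.3, add the visit four weeks after the last dose to the haematology, biochemistry, urinalysis and fasting-glucose lists, dated from each patient's actual last infusion. Early stoppers are then summarised under this visit even when its date matches no listed week.
- For that point, give descriptive change from baseline and shift by arm.
- Show the number of patients contributing in each arm and identify those who entered the open-label extension. Label the table as describing a self-selected subset of the 30 randomised patients.
- If the sponsor prefers to leave the visit out, declare and justify this in SAP section 10.
- In the same edit, settle the starting point of the shift tables: protocol 12.3.2 starts from screening, the SAP from W0.

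The cost is one more column in existing tables and a footnote. No new visit or sample is needed. The small downside is that readers may over-read sparse, selected data, which the counts and the label are meant to prevent.

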7.1.4 Management of missing or incomplete data

Previous and concomitant medications

For the purposes of determining whether a medication was taken during the conduct of the study, any missing or partial start or stop dates for which a definitive determination cannot be made will result in that medication will be assumed to be concomitant, to be conservative.

Linear Mixed Model

Missing data handling for assessing efficacy endpoints using linear mixed model will be described in section 7.4.1.

Adverse Events (AE)

If part of the date/time of an AE is missing, but the existing parts allow determination of timing of AE onset/end relative to start and stop date of the study drug, then the AE will be classified (treatment-emergent or not treatment-emergent) per review of the existing parts of the date/time field. If timing of the AE onset/end relative to start and stop date of the study medication cannot be made, then the AE will be assumed to be a Treatment-Emergent Adverse Event (TEAE).

Vital signs, physical examination, ECG and laboratory values

For absolute, relative changes and shifts from baseline (W0), in case of missing data for the baseline value, the latter will be replaced by the value obtained at screening visit.

CER-001-CLIN-009 CER-001

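### SAP 7.5.3 reverses the Improvement and Deterioration labels in the shift tables for the four positive/negative urine tests

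*SAP*

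**What the plan says.** SAP 7.5.3 promises descriptive statistics, shift tables and absolute changes for every laboratory parameter. Its shift categories are No change (same result at both times), "Improvement (from negative to positive") and "Deterioration (from positive to negative"). The positive/negative parameters are all in the urinalysis list: "Total protein (positive/negative"), glucose, total bilirubin and "Ketones (positive/negative").

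For physical examination and ECG, SAP 7.5.2 sets the direction the other way: "Deterioration (from normal to abnormal CS / from normal to abnormal NCS", with moves from abnormal towards normal counted as Improvement.

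The opening paragraph of SAP 7.5.3 also contains two data rules. A missing W0 value is replaced by the screening value, and "This imputation method will only be applied for generation of shift tables". The next sentence reads "Unreportable values will be replaced by 0". SAP 7.1.4, under a heading that names laboratory values, gives the W0 replacement a wider scope: "For absolute, relative changes and shifts from baseline (W0), in case of missing data for the baseline value", screening is used.

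**The concern.** A shift table is read by its labels. For dipstick-type urine tests a positive is ordinarily the abnormal finding, so the labels as written make a patient who develops proteinuria or bilirubinuria an improver, and one who clears it a deteriorator. Safety over 24 weeks is one of the two primary objectives, and protocol 11.7 names liver and kidney as possible target organs on the basis of toxicology. Urine protein and bilirubin bear on those organs.

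The protocol does not repair the text. Protocol 12.3.2 builds shift tables on normal and abnormal, but the SAP introduction says the SAP takes precedence. A programmer who follows 7.5.3 will therefore code the labels as they stand.

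The two data rules matter less. They leave it open which patients contribute to laboratory absolute changes, and whether a failed assay could enter a summary as a zero.

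**Working it through.** The plan gives no figure to reproduce on this point. The check is a comparison of sections and a count.

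**Which tests the labels govern.** SAP 7.5.3 lists 10 haematology, 20 biochemistry and 10 urinalysis parameters. None of the haematology or biochemistry items is positive/negative, and 4 of the 10 urinalysis items are: total protein, glucose, total bilirubin and ketones. Fasting blood glucose, listed separately, is not marked positive/negative either. The labels therefore have no other test to refer to, and none of the four is a test where a positive would ordinarily be favourable.

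**Direction, section by section.**

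| Change from W0 | SAP 7.5.3 label | Label in the sense of SAP 7.5.2 (positive = abnormal) |
|---|---|---|
| negative to positive | Improvement | Deterioration |
| positive to negative | Deterioration | Improvement |
| no change | No change | No change |

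Both directional labels are reversed. No change is correct.

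**Extent.** The post-baseline visits listed for urinalysis are W4, W8, W16, W24, W32, W40 and W48, which is 7. 4 tests × 7 visits = 28 test-by-visit shift displays.

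**Illustration with assumed counts.** The documents give no event rate. Suppose that in 20 patients at one visit there are 4 new positives, 1 resolution and 15 unchanged. As written, the table prints Improvement 4 (20%) and Deterioration 1 (5%). With the labels swapped it prints Improvement 1 (5%) and Deterioration 4 (20%).

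**What else shows the direction.** SAP 7.1.2 summarises qualitative data by frequency and percentage for each category, and 7.5.3 applies descriptive statistics to all laboratory parameters. The number of positives at each visit is therefore tabulated as well. Microalbuminuria and serum bilirubin are summarised as quantities.

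**Missing W0 value, laboratory absolute change.**
- SAP 7.1.4: use the screening value.
- SAP 7.2 and protocol 12.1: baseline is the most recent value before the first infusion, which also leads to the screening value.
- SAP 7.5.3: replace for shift tables only, so the absolute change is not computed.

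SAP 7.5.3 requires absolute changes, so these rules cannot all be followed. Relative changes are not a laboratory output in 7.5.3, so the conflict concerns absolute changes alone.

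**Zero rule.** Neither document says whether unreportable means below a reporting limit or a failed or absent result, and the sentence is not limited by test or by output. Zero is impossible for sodium, haemoglobin, albumin or pH. If the rule covers failed results, and if the zeros enter the summaries, n − 1 real values with mean m plus one zero give m(n − 1)/n, a fall of 1/n compared with leaving the value missing. With 30 patients randomised 2:1, the arms are 20 and 10, so the fall is 1/20 = 5% or 1/10 = 10%. Both conditions are assumptions, and the documents give no rate of unreportable values.

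**The case against.** Neither document says that positive is the abnormal result. The wording of the labels is certain, while the reversal is an inference from ordinary usage and from the direction in 7.5.2. That is a fair qualification, but no section suggests that a positive urine protein, glucose, bilirubin or ketone result is favourable, so the inference is very strong.

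A reader might go further and infer that a renal or hepatic signal would be hidden or presented as benefit. The documents do not support that. The visit-by-visit frequencies of positives show the true direction, and shift template Table 10 prints the result at the visit above the shift rows, although in normal/abnormal categories. Table review under 7.1.9 and the sponsor-approved dry runs under 12.2 may catch the error. These controls limit the harm but do not correct the text, and double programming covers only the primary endpoint.

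A reader might also want a bias in percentage points. The SAP reports three separate category percentages and computes no net shift, so any such figure would rest on invented counts.

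It is tempting to count SAP 7.5.2 as a further conflicting scope for the W0 replacement, because it names shift tables and absolute changes. Those are the only change outputs in that section, so it gives the same result as 7.1.4.

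The zero rule is an ambiguity and not a shown error. For a result below a reporting limit, or for a count, 0 may be close to the truth.

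**Conclusion.** The label reversal stands and should be fixed. It affects both directional labels for four urine tests at seven visits (28 displays), on the assumption that positive means abnormal. It is a labelling error in descriptive safety tables. No efficacy analysis, hypothesis test or adverse event record changes. Whether the DSMB outputs carry the same labels cannot be known, because SAP section 9 refers to a separate plan that is not among these documents.

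The other two points are minor. The W0 issue is one real conflict, for laboratory absolute changes, between 7.5.3 on one side and 7.1.4 with the baseline definition on the other. The zero rule needs a definition.

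**What to change.** - In SAP 7.5.3, set negative to positive as Deterioration and positive to negative as Improvement. Check that the DSMB plan does not carry the reversed labels.
- State one scope for the screening replacement in laboratory absolute changes, and use it in 7.1.4 and 7.5.3, consistent with the baseline definition in 7.2.
- Define unreportable. Limit replacement by 0 to results below a reporting limit, or to counts, where 0 is a possible value. Name the tests and outputs covered. Keep failed or absent results as missing and count them as missing.

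The cost is a few lines of SAP text and a small programming change before database lock, with no loss of data.
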